3.2 Exclusion Criteria

- 3.2.1 Medical contraindication to receipt of radiotherapy.
- 3.2.2 Severe active co-morbid systemic illnesses or other severe concurrent disease which, in the judgment of the investigator, would make the patient inappropriate for entry into this study or interfere significantly with the proper assessment of safety and toxicity of the prescribed regimens.
- 3.2.3 Uncontrolled intercurrent illness including, but not limited to, ongoing or active infection, symptomatic congestive heart failure, unstable angina pectoris, cardiac arrhythmia, or psychiatric illness/social situations that would limit compliance with study requirements or providing informed consent.
- 3.2.4 Active systemic lupus or scleroderma.
- 3.2.5 Pregnancy.
- 3.2.6 Women of childbearing potential who are unwilling to employ adequate contraception.
- 3.2.7 Prior receipt of ipsilateral breast or chest wall radiation.
- 3.2.8 Recurrent breast cancer.
- 3.2.9 Indications for comprehensive regional nodal irradiation.

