- 16.531 *Quality of life:* The subscales of the BCTOS, elements from CTCAE-PRO, and other patient reported measures such as fatigue, breast pain, breast shape, and arm related morbidity outlined in the appendix will be summarized as the mean \pm SD and median (minimum value, maximum value). Scale score trajectories over time will be examined using stream plots and mean plots with standard deviation error bars overall. Analysis will include percent change from baseline using t-tests and generalized linear models to test for changes at each time point and non-zero slope respectfully.
- 16.532 *Cosmesis:* The values of the cosmesis instruments (patient self-reported and panel-assessed) will be summarized with the frequencies and confidence intervals of fair or poor cosmesis events at baseline, 2 years, and 5 years.
- 16.533 Tumor mutation signatures will be analyzed before and after radiotherapy as compared to pathologic information at the time of surgery. Continuous variable will be compared using unpaired t tests and monimal variables will be compared using contingency tables and Chi square analyses.
- 16.534 Pathologic changes due to preoperative radiotherapy observed at the time of definitive surgery will be described.

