Blistering of the treated breast or chest wall; *response options 0 to 10, 0 = not at all, 10 = blistering as much as could be*

Itching of the treated breast or chest wall; *response options 0 to 10, 0 = not at all, 10 = as itchy as it could be*

Skin burns from radiation on your back; *response options 0 to 10, 0 = not at all, 10 = as itchy as it could be*

11. If you had to do it all over again, would you have this **RADIATION** treatment again?

Yes
No

12. Have you been diagnosed with an infection at your breast cancer surgical site that required treatment with antibiotics or surgery?

Yes
 No

We are interested in your evaluation of your physical appearance and functioning. Please rate the following items from 0 to 10, according to how you feel **AT THIS POINT IN TIME**.

Is the color of your treated breast/chest wall skin different than the other side (red, tan, or lighter)? *response options 0 to 10, 0 = not at all, 10 = as different as it could be*

Do you have visible small blood vessels (spider veins) on your treated breast/chest wall?
response options 0 to 10, 0 = not at all, 10 = as many as it could be

Do you have pain with swallowing? *response options 0 to 10, 0 = not at all, 10 = as painful as could be*

Do you have numbness or a tingling sensation in the arm on the side that was treated?
response options 0 to 10, 0 = not at all, 10 = as much as it could be

Do you have tightness, pulling, or stretching in the arm, breast, or chest area (in the side that was treated?) *response options 0 to 10, 0 = not at all, 10 = as much as it could be*

Do you have tenderness or discomfort on the treated breast/chest wall? *response options 0 to 10, 0 = not at all, 10 = as much as it could be*

Overall, how would you rate the cosmetic results of your breast treatment?
 Excellent Good Fair Poor

Please rate the following items according to your evaluation **at this point in time**:

Breast/chest wall texture (hardening)	 None	 Slight	 Moderate	 Large
Arm heaviness	 None	 Slight	 Moderate	 Large
Shoulder movement	 None	 Slight	 Moderate	 Large

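### Exploratory analyses (low priority): 16.531 tests percent change on items that can be 0 at baseline, and 16.533 names no paired test for the before-versus-after signature contrast in objective 2.33

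*Combined protocol and SAP*

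**What the plan says.** Objective 2.33 has two parts: evaluate tumour mutation signatures before and after radiation, and correlate them with pathology at surgery. Footnote 7 to Section 4.0 plans two tissue samples per patient pre-RT and two at surgery. Section 17.1 qualifies the surgical tumour tissue as subject to availability.

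Section 16.533 covers both parts in one sentence: "Tumor mutation signatures will be analyzed before and after radiotherapy as compared to pathologic information at the time of surgery". It then states the methods: "Continuous variable will be compared using unpaired t tests", with contingency tables and chi-square for nominal variables. No paired method is named for the signatures.

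For patient-reported outcomes, Section 16.531 says: "Analysis will include percent change from baseline using t-tests and generalized linear models to test for changes at each time point". It covers the BCTOS subscales, PRO-CTCAE elements and other "measures such as fatigue, breast pain, breast shape, and arm related morbidity outlined in the appendix". Raw scores are also summarised and plotted over time. No rule is given for a baseline of 0.

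Appendix II uses three kinds of response:

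- **0 to 10, with 0 the absence of the symptom.** Examples are "Do you have numbness or a tingling sensation in the arm on the side that was treated" and "Do you have tenderness or discomfort on the treated breast/chest wall".
- **1 to 10.** Overall quality of life, average pain and average fatigue.
- **Worded answers with no numeric coding given.** Among them are breast/chest wall pain, breast shape and most of the arm items.

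**The concern.** Percent change divides by the baseline score. A symptom-free patient on a 0-to-10 item has a zero denominator and so no value. These are the patients in whom a new symptom would first show, and the change test loses them without the plan saying so.

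The before-versus-after signature contrast is made within patients. An unpaired test treats the two sets of samples as independent. If the two measurements are positively correlated, that test is conservative and can miss a real change. If Section 16.533 means its tests only for signatures versus pathology, then the first part of objective 2.33 has no named test. The section also leaves open whether the pre-RT or the post-RT signature is set against pathology.

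The stake is limited to exploratory objectives 2.31 and 2.33.

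**Working it through.** **What the plan gives.** It states no power, SD, correlation or significance level for the exploratory analyses, so there is no figure of its own to reproduce on this point. The 22 evaluable patients come from Section 16.42. The decision rule built on them (3 or more successes in 22) does reproduce: binomial tail probabilities at 0.05, 0.10, 0.15, 0.20 and 0.25 are 0.095, 0.380, 0.662, 0.846 and 0.939, against 0.09, 0.38, 0.66, 0.85 and 0.94 in Section 16.44. Nothing below changes that rule.

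**Percent change (16.531).** Percent change = 100 × (follow-up − baseline) / baseline. A move from 1 to 4 is +300%; a move from 0 to 4 has no value. If a share p of patients scores 0 at baseline, 22 × (1 − p) keep a value (p is assumed):

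- p = 10%: 22 × 0.9 = 19.8, about 20
- p = 30%: 22 × 0.7 = 15.4, about 15
- p = 50%: 22 × 0.5 = 11
- p = 70%: 22 × 0.3 = 6.6, about 7

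Even at p = 10%, the chance that at least one patient is lost is 1 − 0.9^22 = 0.90. The 1-to-10 items cannot be 0. Worded items are affected only if their lowest answer is coded 0, which the documents do not say.

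**Before versus after (16.533), if the unpaired t test is used.** Assumptions: 22 complete pairs, true shift 0.5 SD, two-sided 5%, normal data, correlation ρ between the two times.

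The true variance of the mean difference is 2σ²(1 − ρ)/n, but the unpaired test works with 2σ²/n. That is too large by a factor 1/(1 − ρ): 1.43, 2.0 and 3.33 at ρ = 0.3, 0.5 and 0.7.

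Paired power follows from a noncentral t with 21 degrees of freedom and noncentrality 0.5 × √(22 / (2(1 − ρ))). At ρ = 0, 0.3, 0.5 and 0.7 the noncentrality is 1.66, 1.98, 2.35 and 3.03, and the power is 0.35, 0.47, 0.61 and 0.82. Simulation agrees, and it supplies the unpaired figures.

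**If surgical samples are missing.** An unpaired test keeps every pre-RT sample; a paired test drops the unmatched ones. With 22 pre and m post samples, all post samples matched, the variance of the mean difference is σ²(1/22 + 1/m − 2ρ/22) for the unpaired contrast and 2σ²(1 − ρ)/m for the paired one. The last two columns use m = 15, assumed missing at random.

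| ρ | Unpaired power, 22 and 22 | Paired power, 22 pairs | Unpaired type I error, 22 and 22 | Unpaired power, 22 and 15 | Paired power, 15 pairs |
|---|---|---|---|---|---|
| 0 | 0.37 | 0.35 | 0.05 | 0.31 | 0.25 |
| 0.3 | 0.35 | 0.47 | 0.02 | 0.28 | 0.33 |
| 0.5 | 0.32 | 0.61 | 0.008 | 0.26 | 0.44 |
| 0.7 | 0.29 | 0.82 | 0.001 | 0.24 | 0.64 |

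The correlation at which the two tests have equal power is about 0.05 with 22 complete pairs, 0.12 with 22 pre and 18 post, and 0.18 with 22 pre and 15 post.

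**The case against.** **The tests in 16.533 may be meant for pathology only.** The sentence before them ends with the comparison to pathology, and objective 2.33 asks to evaluate before and after, which does not promise a test. A reader might infer that the plan prescribes a wrong test for the signatures. The documents do not support that: for pCR versus non-pCR the two-sample tests are appropriate. What stands is that the section merges two contrasts and names a suitable method for only one. The power figures apply only if the unpaired test is used for the other.

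**Pairing is not always better.** This stands. With missing surgical tissue and low correlation, the paired test loses power. Nor does pairing remove selection: a patient with no tumour left gives no post-RT tumour sample, so complete pairs are selected by response.

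**The measures closest to those 16.531 names are mostly not on the 0-to-10 scale.** Fatigue is scored 1 to 10, and breast pain, breast shape and most arm items have worded answers. This narrows the point. Arm numbness or tingling is still a fair example of arm-related morbidity, and tenderness or discomfort is close to breast pain. The extreme case would be "Skin burns from radiation on your back", expected to be near 0 before treatment because "Prior receipt of ipsilateral breast or chest wall radiation" is an exclusion criterion. Section 16.531 does not name that item, so little weight rests on it.

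**A baseline for the 0-to-10 items is inferred.** It follows from the words on change from baseline in Section 16.531; the Section 4.0 grid could not be read here.

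**The slope model.** A reader might also infer that the generalized linear models in Section 16.531 ignore repeated measurements. The term does not exclude a within-patient structure, so no error is shown there.

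**Conclusion.** Both points hold, at low priority.

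The percent-change rule is wrong as written for items that can be 0. Following it drops symptom-free patients from the change test, while the raw summaries and plots keep them. How many are lost depends on a share of zero baselines that the documents do not give.

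The signature point is conditional. Section 16.533 names no suitable test for before versus after. If the unpaired t test were used there, it would be conservative: at an assumed correlation of 0.5 with 22 complete pairs, type I error is about 0.008 and power about 0.32, against 0.61 paired. At zero correlation pairing gains nothing. The correlation, the effect size and the number of pairs are all assumptions.

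A reader might take this as a threat to the trial's conclusion. It is not: no decision, secondary endpoint or safety rule uses these analyses.

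**What to change.** **16.531.** Test absolute change from baseline, at least for every item that can be 0. Percent change may stay for the 1-to-10 items. State the numeric coding of the worded items.

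**16.533.** Separate the two contrasts.

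- *Signatures versus pathology:* keep the two-sample tests, and say whether the pre-RT or the post-RT signature is used.
- *Before versus after:* use a paired t or Wilcoxon signed-rank test for continuous variables and McNemar's test for nominal ones, in patients with both specimens. Name the McNemar version (mid-p or uncorrected), because the exact version is conservative at this size: simulated type I error was 0.024 or lower with 22 pairs.
- Report the number of complete pairs, and how many are missing because no tumour was left.

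**Cost.** A few sentences of SAP text and routine code, with no new data. The paired tests discard unmatched pre-RT samples and lose power below the break-even correlations given above. Settling the choice before the data are seen avoids picking a test afterwards.

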16.6 Data & Safety Monitoring

16.61 The study chair(s) and the study statistician will review the study at least twice a year to identify accrual, adverse event, and any endpoint problems that might be developing. The Mayo Clinic Cancer Center (MCCC) Data Safety Monitoring Board (DSMB) is responsible for reviewing accrual and safety data for this trial at least twice a year, based on reports provided by the MCCC Statistical Office.

16.62 Adverse Event Stopping Rules: The stopping rules specified below are based on knowledge available at study development. We note that the Adverse Event Stopping Rule may be adjusted in the event of either (1) the study re-opening to accrual or (2) at any time during the conduct of the trial and in consideration of newly acquired information regarding the adverse event profile of the treatment(s) under investigation. The study team may choose to suspend accrual because of unexpected adverse event profiles that have not crossed the specified rule below.

Accrual will be temporarily suspended if at any time we observe the following events that are possibly, probably or definitely related to treatment:

If 4 or more patients in the first 10 treated patients or 6 patients at any point in the study experience (end/during radiation, 3 months after radiation, at 12 months and yearly after) a grade 3 or higher skin induced radiation dermatitis, pain over the treated area, swelling over the breast area, pneumonitis, radiation in-field wound infection, or poor cosmetic outcome (change from excellent/good cosmesis to fair or poor, or from fair to poor via Harvard cosmesis scale).

We note that we will review grade 4 and 5 adverse events deemed “unrelated” or “unlikely to be related”, to verify their attribution and to monitor the emergence of a previously unrecognized treatment-related adverse event. However, any grade 4 or higher regardless of the attribution could be used for temporary suspension of the protocol at that time. The study team will review all grade 4 or 5 AEs, if they are clearly “unrelated” the study can remain active while the MCCC reviews the adverse event. In all other cases the grade 4 or 5 toxicity will determine a temporary closure of the study while it is reviewed by the MCCC DSMB.

The study will continue to be monitored by the MCCC DSMB till all patients in the study complete treatment and are followed by 180 days. Patients will continue to be followed and monitored in the study for 5-years by the radiation oncology clinical research team.

16.7 Results Reporting on ClinicalTrials.gov: At study activation, this study will have been registered within the “ClinicalTrials.gov” website. The Primary and Secondary Endpoints (i.e., “Outcome Measures”) along with other required information for this study will be reported on ClinicalTrials.gov. For purposes of timing of the Results Reporting, the initial estimated completion date for the Primary Endpoint of this study is 24 months after the study opens to accrual. The definition of “Primary Endpoint Completion Date” (PECD) for this study is at the time the last patient registered has undergone definitive surgical procedure.

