10.0 Adverse Event (AE) Reporting and Monitoring**10.1 Definitions**

Adverse Event- An untoward or undesirable experience associated with the use of a medical product (i.e. drug, device, biologic) in a patient or research subject.

Serious Adverse Event – Any grade 4 or 5 adverse event as defined by CTC AE v4.0. Adverse events are classified as serious or non-serious. Serious problems/events can be well defined and include in general:

- Death
- Life threatening adverse experience where emergent lifesaving treatment is necessary.

Unanticipated Problems Involving Risks to Subjects or Others (UPIRTSO)- Any unanticipated problem or adverse event that meets the following three criteria:

Serious: Serious problems or events that results in significant harm, (which may be physical, psychological, financial, social, economic, or legal) or increased risk for the subject or others (including individuals who are not research subjects). These include: (1)

death; (2) life threatening adverse experience; (3) hospitalization - inpatient, new, or prolonged; (4) disability/incapacity - persistent or significant; (5) birth defect/anomaly; (6) breach of confidentiality and (7) other problems, events, or new information (i.e. publications, DSMB reports, interim findings, product labeling change) that in the opinion of the local investigator may adversely affect the rights, safety, or welfare of the subjects or others, or substantially compromise the research data, **AND**

Unanticipated: (i.e. unexpected) problems or events are those that are not already described as potential risks in the protocol, consent document, not listed in the Investigator's Brochure, or not part of an underlying disease. A problem or event is "unanticipated" when it was unforeseeable at the time of its occurrence. A problem or event is "unanticipated" when it occurs at an increased frequency or at an increased severity than expected, **AND**

Related: A problem or event is "related" if it is possibly related to the research procedures.

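### The 16.62 suspension rule counts grade 3 or higher in-field wound infection and breast swelling, but Section 10 gives neither a systematic collection route nor a consistent attribution route at grade 3

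*Combined protocol and SAP*

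**What the plan says.** **The rule (16.62).** "Accrual will be temporarily suspended if at any time we observe the following events that are possibly, probably or definitely related to treatment". The thresholds follow: "If 4 or more patients in the first 10 treated patients or 6 patients at any point in the study experience" one of the listed events. These are grade 3 or higher radiation dermatitis, pain over the treated area, "swelling over the breast area, pneumonitis, radiation in-field wound infection, or poor cosmetic outcome". Inside that sentence is a bracketed list of time points: "end/during radiation, 3 months after radiation, at 12 months and yearly after".

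**What is solicited (10.4).** Seven items are graded at baseline and at each evaluation: pain, radiation dermatitis, skin hyperpigmentation, skin hypopigmentation, fibrosis, lymphedema and pneumonitis.

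**What must be submitted beyond that list (10.5).** The visible items cover grade 4 and 5 events and deaths. The serious adverse event definition in 10.1 uses the same cut: "Any grade 4 or 5 adverse event as defined by CTC AE v4.0".

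**Attribution (10.22).** The first sentence requires attribution for grade 4 and 5 events only. The second treats any grade change in a listed event as related. The third has the study PI grade and attribute new unlisted events in or near the irradiated area, with no grade threshold.

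**Forms (18.1).** Solicited adverse events and other adverse events have separate forms. The second is to be completed when applicable.

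**The concern.** A suspension rule works only on the events that reach it. This one starts at grade 3 and requires a judgement of relatedness. For two of the events it names, the sections that should feed it are set differently. Neither event is on the list that sites are told to grade at each evaluation, the visible submission line for unlisted events starts at grade 4, and one sentence on attribution also starts at grade 4.

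At stake is whether the count used for suspension is complete. Every patient is to have surgery in an irradiated breast 4 to 16 weeks after radiotherapy (7.11.2), and the authors thought wound infection and swelling important enough to name. If sites are not prompted for these events, the count depends on who happens to notice and record them. The thresholds are small, so a single missed patient matters.

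**Working it through.** The documents give no operating characteristics for this rule, so there is no stated figure to reproduce. The check sets the sections side by side for each event that 16.62 counts.

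| Event in 16.62 | Named in 10.4? | Visible 10.5 line if unlisted | Attribution at grade 3 under 10.22 |
|---|---|---|---|
| Radiation dermatitis | Yes | Not needed | Related by default on a grade change |
| Pain over the treated area | Yes, as pain | Not needed | Related by default on a grade change |
| Pneumonitis | Yes | Not needed | Related by default on a grade change |
| Swelling over the breast area | Not by name; lymphedema is nearest | Grade 4-5 only | Not required (sentence 1); by the PI (sentence 3) |
| In-field wound infection | No | Grade 4-5 only | Not required (sentence 1); by the PI (sentence 3) |
| Poor cosmetic outcome | Separate scale (11.3.1, 16.3) | Not applicable | Not applicable |

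**Step 1, solicitation.** Three of the five graded adverse events are solicited: 5 − 3 = 2 are not named. Wound infection is a firm mismatch. Swelling is a mismatch unless lymphedema is meant to include the breast, which no section says.

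**Step 2, grade cut.** The rule counts from grade 3. The visible requirement for unlisted events starts at grade 4, as does the serious adverse event definition. A grade 3 event of either kind lies between the two cuts.

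**Step 3, attribution.** 16.62 counts only events at least possibly related. For a grade 3 unlisted in-field event, the first sentence of 10.22 removes the requirement to attribute and the third supplies it. Section 10.21 also asks whether each event is related. The text needs reconciling, but an attribution route exists.

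**Step 4, other routes.** Section 10.3 has a worksheet and log completed once an event has been identified. The form for other adverse events in 18.1 shows no grade limit. The analyses in 16.521 and 16.522 cover all adverse event types. Appendix II asks patients about surgical-site infection and breast swelling, but yields no CTCAE grade or attribution. These routes can record a noticed event. None has staff ask about and grade these two terms at each evaluation.

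**Step 5, leverage.** With 3 counted patients in the first 10 and one affected but uncounted, the count is 3 and not 4, so the first limb does not trigger. With 5 counted overall and one uncounted, the count is 5 and not 6. Maximum accrual is 25 (16.42).

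**The case against.** The strongest reply is that a site must follow all of Section 10. Under the third sentence of 10.22, a new in-field event goes to the PI for grading and attribution at any grade. Section 10.5 is a reporting clause and does not limit collection; the investigator reviews all adverse event reports and monitors the severity and frequency of non-UPIRTSO events (10.312). This stands. A reader might infer that a grade 3 wound infection would go unrecorded, or that a site may withhold one it has noticed. The documents do not support either reading.

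Second, 10.22 can be read coherently: listed events are related by default, unlisted in-field events are attributed by the PI, and the grade 4-5 sentence governs the rest. That reading is reasonable, but the first sentence carries no such restriction.

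Third, the visible numbering passes from 10.5 to 10.52, so an item may be missing from the text available here. The submission point is therefore limited to what is visible. A restored item would not by itself put either event on the solicited list in 10.4.

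Fourth, there are backstops. "The study team may choose to suspend accrual because of unexpected adverse event profiles that have not crossed the specified rule below". The study chair, the statistician and the DSMB each review the trial at least twice a year, and DSMB monitoring runs "till all patients in the study complete treatment and are followed by 180 days". The DSMB works "based on reports provided by the MCCC Statistical Office", however, and those reports depend on what was collected. The backstops limit the gap without closing it.

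Finally, the bracketed time points might suggest that events seen at other visits do not count. The opening sentence of the rule sets no time limit, and the list closely follows the provider cosmesis schedule in 16.3, so it may apply to cosmesis alone. The assessment table in Section 4.0 is not readable here, and no gap in assessments is claimed.

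**Conclusion.** The point holds as a misalignment between the suspension rule and the sections that supply its data. In-field wound infection, and breast swelling unless lymphedema is meant to cover it, count toward suspension from grade 3. Neither is solicited by name, and their submission and attribution at grade 3 are not consistently required. Capture is unsystematic rather than absent, and the rule can undercount.

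The size is one of five graded adverse events for certain, and two at most. How much this would change the chance of suspension cannot be stated: the documents give no event rates, no share for these two terms and no expected rate of missed events. A reader might infer a specific loss of sensitivity in the rule, but any figure would rest on invented inputs.

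The conclusion assumes that the seven rows of 10.4 are complete as shown and is limited to the visible text of 10.5. It does not question the thresholds. It is a cheap safety improvement that should be made.

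**What to change.** 1. Add wound infection and breast swelling or edema as rows in 10.4, so that both are graded at baseline and at each evaluation.
2. In 10.5 and 10.22, require submission and attribution of every grade 3 or higher event named in 16.62.
3. Reconcile the first and third sentences of 10.22 with each other and with 16.62. State whether the default related attribution for listed events applies to a postoperative wound infection.
4. As a minor wording point, state in 16.62 whether the bracketed time points apply to all events or to cosmesis alone.

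The thresholds are unchanged. The cost is two more rows on an existing form, at evaluations already planned, and a few sentences of text. There are two downsides. The rule may trigger somewhat more often. And once wound infection is listed, a grade change would count as related under 10.22 even where surgery alone may explain it, unless item 3 addresses this.
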